10.2.2 Adverse Event Overview

An overview of AEs will be presented consisting of the number and percentage of subjects experiencing at least one event for each of the following AE categories:

- Any TEAE
- Any TEAE related to study drug according to the investigator
- Any severe TEAE
- Any serious TEAE
- Any TEAE leading to discontinuation of study drug
- Any TEAE leading to interruption of study drug
- Any TEAE leading to death
- TEAEs of Special Interest
- All deaths
 - Deaths occurring \leq 30 days after last dose of study drug
 - Deaths occurring $>$ 30 days after last dose of study drug

10.2.3 Treatment-Emergent Adverse Events by SOC and/or PT

TEAEs will be summarized by SOC and PT; by maximum relationship to study drug as assessed by the investigator (e.g., reasonable possibility or no reasonable possibility) and SOC and PT; by maximum severity and SOC and PT; and by subject number and SOC and PT. Specific AEs will be counted once for each subject for calculating percentages, unless stated otherwise. In addition, if the same AE occurs multiple times within a

subject, the highest severity and level of relationship to investigational product will be reported.

In addition, TEAEs will be summarized by PT and sorted by decreasing frequency for the linaclotide treatment group.

10.2.4 Deaths, Serious Adverse Events, and Adverse Events Leading to Study Treatment Discontinuation

Treatment-emergent serious adverse events (SAEs) (including deaths), TEAEs leading to premature discontinuation of study drug, and TEAEs leading to death will be summarized by SOC and PT.

Tabular listings will be provided for all deaths, all SAEs, TESAEs, TEAEs leading to death, TEAEs leading to premature discontinuation of study drug, and TEAEs leading to study drug interruptions.

10.2.5 Treatment Emergent Adverse Events of Special Interest

The treatment emergent adverse events of special interest (AESIs) including significant volume depletion and/or significant electrolyte abnormalities and /or ECG abnormalities that are considered by the investigator or sponsor to be related to diarrhea will be monitored throughout this study.

The number and percentage of subjects with AESIs during the study will be tabulated by preferred term. AESIs will also be provided in a listing.

10.3 Analysis of Laboratory Data

Data collected from central and local laboratories, including additional laboratory testing due to an SAE, will be used in all analyses, except for Baseline where SAE-related laboratory assessments on or before the first dose of study drug will be excluded. The clinical laboratory tests defined in the protocol operations manual (e.g., hematology, clinical chemistry, urinalysis) will be summarized.

Each laboratory variable will be summarized for all time points (starting with Baseline) with the number of non-missing observations, mean and standard deviation, median, minimum and maximum. Mean change from baseline to each applicable postbaseline visit will be summarized for selected laboratory variables, with the number of observations, baseline mean, and visit mean. The change from baseline mean, standard error, and 95% confidence interval will be presented for the mean change from baseline within each treatment group.

Changes in laboratory parameters will be tabulated using shift tables categorized as low, normal, or high based on the normal ranges of the laboratory used for each sample. A shift table from baseline to minimum and maximum value (based on normal range) will be created. A similar shift table will be provided to summarize shifts from baseline to the final postbaseline value.

Laboratory abnormalities meeting CTC criteria grade 3 and 4, with a grade worsening compared to baseline, will be summarized. Toxicity grading scale is based on National Cancer Institute Common Toxicity Criteria (NCI CTC) AE version 4.03. The number and percentage of subjects who have a laboratory value meeting the criteria will be summarized by treatment group. Listings will be provided to summarize subject-level laboratory data for subjects meeting the criteria.

Laboratory abnormalities will be evaluated based on Potentially Clinically Important (PCI) criteria ([Appendix C](#)). For each laboratory PCI criterion, the number and percentage of subjects who have a laboratory value meeting the criteria will be summarized by treatment group. Listings will be provided to summarize subject-level laboratory data for subjects meeting PCI criteria. The percentages will be calculated relative to the number of subjects with available non-PCI baseline values and at least 1 postbaseline assessment for the assessment period. The numerator will be the total number of subjects with available non-PCI baseline values and at least 1 PCI postbaseline assessment for the assessment Period. A supportive tabular display of subject with PCI postbaseline values will be provided.

Potential Hy's Law

Potential Hy's Law criteria within a 24-hour window is defined by a postbaseline elevation of ALT or AST $\geq 3 \times$ ULN, along with TBL $\geq 2 \times$ ULN and a non-elevated ALP $< 2 \times$ ULN, all based on blood draws collected within a 24-hour period.

Subjects who meet the potential Hy's Law criteria from the first dose of study drug to within 30 days after the last dose of treatment will be summarized. Supportive tabular displays will also be provided.

Assessment of Liver Enzyme and Bilirubin Elevations

The liver-specific laboratory tests include the serum glutamic pyruvic transaminase (SGPT/ALT), serum glutamic-oxaloacetic transaminase (SGOT/AST), alkaline phosphatase (ALP), and total bilirubin (TBL). The frequencies and percentages of subjects with post baseline liver specific function test values that meet the following criteria of potential clinical interest will be summarized by treatment group:

- ALT $\geq 3 \times$ ULN
- ALT $\geq 5 \times$ ULN
- ALT $\geq 10 \times$ ULN
- ALT $\geq 20 \times$ ULN
- AST $\geq 3 \times$ ULN
- AST $\geq 5 \times$ ULN
- AST $\geq 10 \times$ ULN
- AST $\geq 20 \times$ ULN
- TBL $\geq 2 \times$ ULN
- ALP $\geq 1.5 \times$ ULN
- ALT or AST $\geq 3 \times$ ULN
- ALT and/or AST $\geq 3 \times$ ULN and TBL $\geq 1.5 \times$ ULN
- ALT and/or AST $\geq 3 \times$ ULN and TBL $\geq 2 \times$ ULN
- ALT or AST $\geq 5 \times$ ULN for more than 2 weeks

- ALT or AST $\geq 8 \times$ ULN

where ULN is the upper normal limit. The maximum ratio relative to the ULN will be used to determine if subjects meet any of the criteria listed above.

A listing of potentially clinically significant liver function laboratory values will be provided. The listing will include all subjects who meet any of the following 4 criteria:

- ALT $\geq 3 \times$ ULN, or
- AST $\geq 3 \times$ ULN, or
- ALP $\geq 1.5 \times$ ULN, or
- TBL $\geq 1.5 \times$ ULN.

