APPENDIX D. ACTIVITY SCHEDULE

The following table shows the required activities. The individual activities are described in detail in the **Operations Manual**. Allowed modifications due to COVID-19 are detailed in the Operations Manual.

Study Activities Table – All

Activity	Screening		Preintervention	Study Intervention Period (28 days)		EOT visit or premature discontinuation	Postintervention (7 days)
	Day -28 to Day 0	Day 1		Enrollment / Randomization	Day 2		
Visit	1	2	3	4	5	6	7
INTVIEWS & QUESTIONNAIRES							
LAR/Parent/guardian Informed consent	✓						
Eligibility criteria	✓	✓	✓				
Rome IV Assessment	✓					✓	
Assess Rome IV status			✓	✓	✓		
Medical/surgical history	✓						
Lifestyle Modification Information given to LAR/Parent/Guardian		✓					
Adverse event assessment	✓	✓	✓	✓	✓	✓	
Prior/concomitant therapy	✓	✓	✓	✓	✓	✓	
OBSERVER-REPORTED OUTCOMES							
eDiary and Instructions Given to the LAR/Parent/Guardian/Caregiver		✓					
Review eDiary data and complete manual review of subject eligibility			✓				
eDiary Compliance			✓	✓	✓	✓	
Return eDiary Device							✓

Activity	Screening		Preintervention	Study Intervention Period (28 days)		EOT visit or premature discontinuation	Postintervention (7 days)	
	Day -28 to Day 0	Day -21 to Day -14		Day 1	Enrollment/ Randomization	Day 15 (± 2 Days)	Week 2	Week 4
Visit	1	2	3	4	5	6		
EXAMS								
ECG (single)	✓					✓		
Height	✓							
Vital signs (including weight) and Postural Vital Signs	✓	✓	✓	✓	✓	✓	✓	
Physical examination	✓		✓	✓	✓			
Fecal Impaction Assessment	✓	✓	✓					
CENTRAL LABS								
Clinical chemistry, Hematology (CBC)	✓					✓		
Optional Blood samples for PK assay (refer to Appendix G)				✓ (optional)	✓ (optional)			
TREATMENT								
IWRS (registration of screening and enrollment)	✓		✓					
Randomization/drug assignment (Part 2 only)			✓					
Rescue Medication	✓	✓	✓	✓	✓			
Study drug administered in the clinic			✓					
Study drug Dispensed			✓					
IP Compliance and Accountability				✓	✓			

AE = adverse event; ECG = electrocardiogram; eDiary = electronic diary; EOS = end of study; EOT = end of treatment; IWRS = interactive Web response system; LAR = legally authorized representative; ObsRO = observer reported outcome

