APPENDIX E. LIVER SAFETY: SUGGESTED ACTIONS AND FOLLOW-UP ASSESSMENTS

Close monitoring should be initiated for the following subjects:

- Subjects with normal baseline serum AT who develop an increase of serum AT $\geq 2 \times$ ULN
- Subjects with elevated baseline AT who develop an increase of serum AT $> 2 \times$ the baseline value

The subject should return to the study site and be evaluated for potential drug-induced liver injury (DILI) as soon as possible, preferably within 48 to 72 hours from the time the investigator becomes aware of the abnormal results. Evaluation should typically include repeat testing of all 4 of the usual serum biochemical measures (alanine aminotransferase [ALT], aspartate aminotransferase [AST], alkaline phosphatase, and total bilirubin) to confirm the abnormalities and to determine if they are increasing or decreasing.

If it is difficult for the subject to return to the study site promptly, the subject should be retested locally, but normal laboratory ranges should be recorded, results should be made available to sponsor's study physician and the investigator immediately, and the data should be included in the eCRF. If repeat testing within this time frame is not possible, the study intervention should be discontinued.

It is critical to initiate close monitoring immediately upon detection and confirmation of signals of potential DILI as early as possible and not to wait until the next scheduled visit or monitoring interval. Close monitoring of the subject should be initiated in conjunction with the sponsor and consideration given to the following:

- Obtain a more detailed history of symptoms and prior or concurrent diseases.
- Obtain a history of concomitant drug use, including nonprescription medications, herbal products and dietary supplements, alcohol and recreational drug use, and special diets.
- Obtain a history of exposure to environmental chemical agents.
- Initiation of appropriate evaluations including applicable laboratory tests (e.g., direct bilirubin, international normalized ratio [INR]), physical assessments, and other assessments (e.g., imaging)
 - Rule out other potential causes of biochemical abnormalities, e.g., acute viral hepatitis types A, B, C, D, and E; autoimmune or alcoholic hepatitis; non-alcoholic steatohepatitis; hypoxic/ischemic hepatopathy; and biliary tract disease.
- Consider gastroenterology or hepatology consultations.

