3.15 Clinical Laboratory Tests

A certified laboratory will be utilized to process and provide results for the clinical laboratory tests. Laboratory reference ranges, including reference ranges from the local laboratory (to be used in the event of a safety event or if lab kits from the central laboratory are not available), will be obtained prior to the initiation of the study.

Instructions regarding the collection, processing, and shipping of these samples will be provided by the central laboratory. Please note: Blood collection from heel-, finger-, or ear-stick may contain interstitial/tissue fluid, and therefore are not acceptable. Blood should only be collected from a vein, blood should not be collected from a heel-, finger-, or ear-stick.

If a laboratory test value is outside the reference range and the investigator considers the laboratory result to be clinically significant, the investigator will:

- repeat the test to verify the out-of-range value;
- follow the out-of-range value to a satisfactory clinical resolution; or
- discontinue the subject from the study or require the subject to receive treatment; in this case, the laboratory result will be recorded as an adverse event.

Clinical Chemistry

A fast is not necessary for blood samples to be drawn for chemistry.

The baseline laboratory test results for clinical assessment for a particular test will be defined as the last measurement prior to the initial dose of study drug.

The maximum volume of blood collected from each subject over the duration of the study for clinical laboratory testing (which includes chemistry and hematology panels) will not exceed 13.5 mL. Repeat or unscheduled samples may be taken for safety reasons or for technical issues with the sample.

Clinical Laboratory Tests ^a		
Hematology	Clinical Chemistry ^b	Other Screening Tests
Platelet count (estimate not acceptable)	Blood urea nitrogen (BUN/Urea)	
Red blood cell (RBC) count	Creatinine	
Hematocrit	Glucose non-fasting	
Hemoglobin	Potassium	
RBC indices:	Sodium	
MCV	Chloride	
MCH	Bicarbonate/CO ₂	
MCHC	Magnesium	
White blood cell (WBC) count with differential absolute:	Phosphate	
Neutrophils	Total protein	
Lymphocytes	Total bilirubin	
Monocytes	Calcium	
Eosinophils	Alanine transaminase (SGPT/ALT)	
Basophils	Aspartate transaminase (SGOT/AST)	
	Alkaline phosphatase	
	Total, direct and indirect bilirubin	
	Total cholesterol	
	Albumin	

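### SAP 10.3 decides all 15 listed liver criteria from the maximum ratio to ULN, which cannot establish the row for ALT or AST ≥5 × ULN lasting more than 2 weeks

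*SAP*

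**What the plan says.** SAP Section 10.3, under the assessment of liver enzyme and bilirubin elevations, lists 15 criteria to be summarised as counts and percentages by treatment group. It closes the list with one derivation rule: "The maximum ratio relative to the ULN will be used to determine if subjects meet any of the criteria listed above".

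The 15 rows fall into three kinds:

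- 12 single-threshold rows: ALT at 3, 5, 10 and 20 × ULN; AST at the same four levels; TBL at 2; ALP at 1.5; ALT or AST at 3; ALT or AST at 8.
- 2 combined rows: ALT and/or AST ≥3 × ULN with TBL ≥1.5 × ULN, and "ALT and/or AST $\geq 3 \times$ ULN and TBL $\geq 2 \times$ ULN".
- 1 duration row: ALT or AST ≥5 × ULN "ULN for more than 2 weeks".

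The potential Hy's Law definition stands just before this list and has its own timing condition: "all based on blood draws collected within a 24-hour period".

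The Activity Schedule (Protocol Appendix D) and the Operations Manual visit lists place clinical chemistry at Screening and at Week 4/EOT (Visit 5). Other samples can exist. Operations Manual 3.15 states: "Repeat or unscheduled samples may be taken for safety reasons or for technical issues with the sample". Protocol Appendix E calls for re-evaluation of a child with raised transaminases, "preferably within 48 to 72 hours from the time the investigator becomes aware of the abnormal results", with repeat testing "to confirm the abnormalities and to determine if they are increasing or decreasing". SAP 10.3 brings central and local results, and testing prompted by an SAE, into the analyses.

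**The concern.** The closing rule covers the whole list without exception, but a maximum answers only one question: how high did the value go? That suits the 12 single-threshold rows. It does not suit a row about how long a value stayed high, and it says nothing about whether two analytes were high at the same time.

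For the duration row, the literal rule removes the condition that distinguishes the row. A brief rise that is normal at retest is then tabulated as a rise lasting more than 2 weeks. A reader of the table also cannot tell whether a zero means that no child had a sustained rise or that no child had the samples to show one.

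For the two combined rows, the rule pairs each child's highest ALT/AST with that child's highest TBL, whatever the dates. Unlabelled, such a row invites a reader to take the two peaks as simultaneous.

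What is at stake is the accuracy of a few liver-safety counts in a new infant population, reported in very small groups.

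**Working it through.** The plan gives no figure to reproduce here. The check applies the stated rule, and then a rule based on dated draws, to the listed criteria.

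**Inputs from the documents.** The maximum-ratio rule, the 15 criteria and the 24-hour Hy's Law window are in SAP 10.3. Chemistry timing is in Protocol Appendix D and the Operations Manual visit lists. Group sizes are in Protocol 4.1 and SAP 2.3: 6 per Part 1 cohort, and 12 in Part 2 at 1:1, so 6 per arm.

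**Step 1: is there a persistence or concurrency rule elsewhere?** SAP Appendix B derives diary variables only. SAP Appendix C gives single-value thresholds. Neither adds a rule for the duration row or the combined rows.

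**Step 2: what can the scheduled data show?** There is one scheduled post-baseline chemistry draw per cohort, at Day 29. One draw cannot show a duration under any rule. A run starting on Day 29 needs a further value more than 14 days later: 29 + 14 = 43, so Day 44 or after. The last scheduled visit (Visit 6) falls 7 days, plus up to 2, after Visit 5 and has no chemistry. The duration row therefore depends wholly on repeat, local or other unscheduled samples. With the single scheduled draw, ALT/AST and TBL come from the same sample, so pairing across days also requires extra samples.

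**Step 3: worked cases.** The values are assumptions chosen to test the logic. TBL is 0.8 × ULN in A, B and E and at C's first draw; ALP is 0.9 × ULN throughout. The date-based duration rule requires values ≥5 × ULN spanning more than 14 days with none below 5 × ULN between.

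| Child | Values (× ULN) | Duration row, maximum rule | Duration row, dated values | Combined row (TBL ≥2), maximum rule | Combined row, same draw | Hy's Law, 24 h |
|---|---|---|---|---|---|---|
| A | ALT 5.2 Day 29; 1.0 Day 32 | yes | no | no | no | no |
| B | ALT 5.2 Day 29; 5.1 Day 46 | yes | yes | no | no | no |
| C | ALT 3.4 Day 29; ALT 1.4 and TBL 2.1 Day 36 | no | no | yes | no | no |
| D | ALT 3.4 and TBL 2.1, both Day 29 | no | no | yes | yes | yes |
| E | ALT 5.2 Day 29, no other draw | yes | cannot be shown | no | no | no |

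A, B and E all fill the duration row under the maximum rule. Only B has a run longer than 14 days (46 − 29 = 17). Under the literal rule the row equals the union of the ALT ≥5 and AST ≥5 rows. E shows that this needs no retest: one high value at Visit 5 is enough.

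C and D both fill the combined row under the maximum rule. Only D has concurrent values, and only D meets the Hy's Law definition.

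**Step 4: size.** One child is 1/6 = 16.7% of a cohort or arm, and 1/12 = 8.3% of a same-dose pool of 12.

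**The case against.** The strongest reply on the duration row is that the criterion keeps its own words. On that reading the closing sentence fixes only which multiple of ULN is used, and the programmer would still check the duration. This is a fair account of what was probably meant. But the sentence says the maximum determines whether a subject meets any listed criterion, and no other text says how to check a duration. Even the kind reading leaves the row without a derivation or a statement of who is evaluable.

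On the combined rows the reply largely succeeds. They are offered as criteria of potential clinical interest, beside a strict concurrent definition. A child who appears in the screen but not under Hy's Law is what a sensitive screen produces; it is not a contradiction. A 24-hour window would bring the TBL ≥2 × ULN row close to the Hy's Law definition, differing only in the ALP condition. What remains is the need for a label.

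The reply is also right about consequences. Safety results are descriptive. No stated escalation or stopping rule refers to these rows: the AESIs concern diarrhea-related events, and liver monitoring under Protocol 5.5 and Appendix E works from individual results. Every child in the three affected rows has ALT or AST ≥3 × ULN and so enters the liver listing at the end of SAP 10.3, where the case can be checked if dates and repeat values are printed, a format the SAP does not specify. This helps the reader but does not correct the count.

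**Conclusion.** The point holds for the duration row. Read as written, the rule classifies a single value ≥5 × ULN as lasting more than 2 weeks, and the scheduled draws cannot supply the missing information. For the two combined rows the point is one of labelling.

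Three stronger readings are tempting, and the documents do not support them:

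- **All liver assessment in SAP 10.3 rests on maxima.** Potential Hy's Law has its own 24-hour rule, and for 12 of the 15 listed rows a maximum is the correct tool.
- **The combined rows conflict with Hy's Law and must take the 24-hour window.** An unwindowed screen beside a strict definition is defensible, so imposing the window is a preference.
- **The duration row should be a percentage of children with long enough follow-up.** Retests are prompted by abnormal values (Protocol Appendix E), so that denominator is selected on the outcome and could report 1/1 = 100%.

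The size is one child per misclassification, 17% of a group of 6 or 8% of a same-dose pool of 12, in descriptive counts only. For the duration row it arises only if a child has a value ≥5 × ULN that was not sustained or was not followed. For the combined rows it arises only if extra samples separate the peaks. The documents give no expected rate of such elevations, and there may be none.

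**What to change.** In SAP 10.3, before database lock:

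1. Limit the maximum-ratio rule to the 12 single-threshold rows.
2. Derive the duration row from dated values: consecutive ALT or AST results ≥5 × ULN spanning more than 14 days, with none below 5 × ULN between. Keep the full group as the denominator and print beside the count the number evaluable, meaning children with at least two post-baseline results more than 14 days apart. Alternatively, drop the row, given the single scheduled post-baseline draw.
3. Label the two combined rows as peak values that are not necessarily concurrent, or flag which of the counted children had both values in the same draw or within 24 hours.

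The cost is a few sentences in the SAP and minor programming. No new data are needed and no other output changes.

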10.4 Analysis of Vital Signs

Descriptive statistics for vital signs (i.e., temperature, body weight, height, respiratory rate, supine pulse rate, supine systolic and diastolic blood pressure) and changes from baseline values at each assessment time point will be presented by treatment group.

Vital sign values will be considered PCI if they meet both the observed-value criteria and the change-from-baseline criteria listed in Table C-4. The number and percentage of subjects with PCI postbaseline values will be tabulated by treatment group for the double-blind intervention period separately. The percentages will be calculated relative to the number of subjects with available non-PCI baseline values and at least 1 postbaseline assessment in the specific period. The numerator will be the total number of subjects with available non-PCI baseline values and at least 1 PCI postbaseline value during the specific period for the corresponding cohort. A supportive tabular display of subjects with PCI postbaseline values will be provided, including the PID number, baseline and all postbaseline (including non-PCI) values.

